10.2.3 Low Level Risks

Low Level Risk does not indicate the likelihood the event will occur but indicates per the RACT assessment that no new or complex procedures are needed to ensure screening is adequate to eliminate or manage the risk in the patient population.

10.2.3.1 Thermoregulatory Risks and Mitigation

MDMA administered in a controlled setting produces only a slight increase in body temperature [110]. Ambient temperature does not enhance or attenuate this slight elevation in humans. In data gathered from sponsor-supported Phase 2 studies, it was found that compared to placebo, a higher percentage of participants receiving MDMA had peak body temperatures greater than 1 degree Celsius (°C) above Baseline. However, there was no strong relationship between dose of MDMA and peak body temperature or between MDMA dose and elevation above threshold of 1°C above Baseline.

Ambient temperature will be kept at a comfortable level during Experimental Sessions. If a participant's temperature rises more than 1°C or the participant states that they feel hot, attempts will be made to decrease body temperature and increase comfort by removing blankets and layers of clothing, decreasing the ambient temperature, and, if necessary, directing a fan toward the

participant. If at any time the temperature rises more than 1.5°C above Baseline despite these efforts, the site physician will be consulted for further evaluation and treatment.

10.2.3.2 Osmoregulatory Risk and Mitigation

MDMA administered in a controlled setting is not expected to have any risks of osmoregulatory changes. Participants will not be allowed to drink more than three liters of electrolyte-containing fluids over the course of the Experimental Session and fluid intake will be spread out appropriately during the session. If a participant exhibits any signs of toxicity or clinically significant dilutional hyponatremia despite these precautions after an Experimental Session, they will not receive another Experimental Session unless it is approved by the investigator, site physician, and the Medical Monitor.

10.2.3.3 Genotoxicity Risk and Mitigation

To reduce the risk of metabolic activation and formation of nitroso-derivatives of MDMA due to interactions with nitrates or nitrites in food, participants are required to have fasted (no intake other than alcohol-free liquids) for 10 hours prior to IMP administration at Experimental Sessions.

10.2.3.4 Reproductive and Developmental Risks and Mitigation

Risks posed by MDMA to pregnant people are not known. One of two studies of Ecstasy users suggests that use of Ecstasy and other drugs during pregnancy may be associated with some abnormalities at birth while the other failed to find this association [111, 112].

Pregnant and lactating people will be excluded from participation in the study. Participants who are able to become pregnant must have a negative pregnancy screen before undergoing each Experimental Session and must agree to use adequate birth control for the duration of the study during the Treatment Period. Paternal drug exposure studies show that exposure to MDMA was not a factor in adverse pregnancy outcomes, so partners of participants who were assigned male at birth will not be required to practice birth control. Due to the limited number of single-dose exposures being studied in this trial, the chance of birth defects are low. Procedures described in [Section 11.3 Pregnancy](#) have been put in place to mitigate risk of reproductive or developmental exposure to the IMP.

10.2.4 Minimal Risks

Minimum Level Risk does not indicate the likelihood the event will occur but indicates per the RACT assessment that no procedures are needed beyond basic monitoring to ensure screening is adequate to eliminate or manage the risk in the patient population.

10.2.4.1 Common AEs

Common AEs are typically observed during IMP administration, but are transient and diminish as the IMP is metabolized and excreted over the next 72 hours after dosing. Common AEs most frequently reported during Experimental Sessions include muscle tightness in the jaw, lack of appetite, dizziness, and nausea. During the week following treatment, lack of appetite, muscle tightness in the jaw, restlessness, weakness, dry mouth, thirst, impaired gait/balance, and sensitivity to cold may be reported. Severe anxiety, insomnia, fatigue, and depressed mood are commonly reported in PTSD studies in both placebo and MDMA groups. Common AEs are typically self-limiting. Elevations in anxiety and poor sleep respond to management with short-

acting low dose benzodiazepines (specifically, lorazepam) or sleep aids as needed, per clinical judgment of the site physician.

10.2.4.2 Potential Neurotoxicity Associated with Ecstasy Use

Some researchers believe that MDMA is neurotoxic in humans even at doses used in clinical trials [113]. However, these claims are based on studies that employed inappropriately high doses of MDMA utilized in animal studies and on human studies comparing the effects of repeated use of Ecstasy, often along with other drugs. Meanwhile, another recently published meta-analysis has taken careful steps to overcome methodological limitations in previous work and found only modest evidence of neurotoxicity [114]. The sponsor has carefully considered the risks of such neurotoxicity and conclude that they are minimal in the proposed study. This conclusion is supported by empirical and toxicokinetic evidence and is consistent with the lack of toxicity reported in previous clinical MDMA studies. It does not appear that MDMA-assisted psychotherapy negatively impacts cognitive function. Neurotoxicity and neurocognitive effects of MDMA were studied in the sponsor's Phase 2 studies and provided sufficient data to conclude that limited exposures to MDMA allowed for adequate time for reversibility of any effects at the synaptic level. Furthermore, limited dosing of MDMA has shown to have no effect on neurocognitive functioning.

10.2.4.3 Abuse Liability

Findings in humans and animals suggests that MDMA possesses moderate abuse potential that is higher than that reported for "classic hallucinogens," like psilocybin, but lower than that reported for psychostimulants, such as cocaine or methamphetamine. In sponsor-supported Phase 2 PTSD studies in 107 participants treated with MDMA-assisted psychotherapy in a controlled clinical setting, 29.9% (32 of 107) of participants had tried Ecstasy at least 6 months prior to enrollment, with U.S. samples demonstrating a higher prevalence of use than international studies.

Participants reported using Ecstasy an average of 2.3 (SD:1.43) times. Due to the known association of substance use disorders and PTSD, this sample was likely not representative of the general healthy volunteer population but is congruent with the PTSD population. At long-term follow-up across Phase 2 studies, 8.7% of participants (eight of 92) reported "Ecstasy" use across studies, with five participants indicating single and not repeated use and three participants indicating two uses. Six of these eight subjects had used Ecstasy prior to study participation. Of these participants, most were attempting to recreate a therapeutic experience, and most did not indicate a desire to repeat this. In addition to self-report data, urine drug screens specific for MDMA were performed at random and 2, 6, and 12 months after the final Experimental Session during one study (MP2, N=12). All were negative, supporting the observation that study participants did not seek out MDMA or Ecstasy after taking part in the study [60]. In addition to data on Ecstasy use at follow-up, AEs were reviewed across Phase 2 studies, the sponsor found an absence of clinically significant AEs supporting drug dependence, intentional drug misuse, and substance abuse, and a low rate (<2%) of secondary terms that reflect acute intoxication.

Based on current information, it does not appear that MDMA-assisted psychotherapy demonstrates signals associated with known abuse liability patterns in a PTSD population when administered in a therapeutic setting under continuous observation in three single-dose sessions. Any abuse potential and diversion is further limited since the IMP is not supplied to the participant to take home and is administered in a restrictive setting. Each investigator responsible for dispensing or administration of the IMP will maintain current registration with authorities with oversight of controlled substances. IMP will be handled following all regulations pertaining to the handling and dispensing of controlled substances within research studies. See [Section 11.1.1](#) for AESI terms.

Within-participant elevation in self-reported Ecstasy use post-treatment will be clinically assessed for signals of abuse and will be monitored during the Long-term Follow-up extension study associated with this protocol.

11.0 Safety

11.1 Adverse Events

In accordance with guidance for the specific study site, Health Canada Clinical Safety Data Management Definitions and Standards for Expedited Reporting International Conference on Harmonisation (ICH) Topic E2A: Guidance for Industry or FDA Safety Reporting Requirements for INDs and BA/BE Studies, an Adverse Event (AE) is defined as any medical occurrence in a participant, including any abnormal sign (e.g., abnormal physical exam or laboratory finding), symptom, or disease, temporally associated with the participant's involvement in the research, whether or not considered related to participation in the research. This definition includes concurrent illnesses or injuries and exacerbation of pre-existing conditions.

Events related to planned treatments or physician visits for Baseline conditions collected in the medical history will not be collected, unless there is an exacerbation of the condition, in which case they will be actively followed until resolution.

An unexpected AE is one that is not listed in the current IB or an event that is by nature more specific or more severe than a listed event.

The site physician will be responsible for reviewing and confirming all AEs and SAEs collected during the study. The therapy teams will collect AEs during study visits from Enrollment (Visit 0) through Study Termination (Visit 20). Participants will be asked directly how they are feeling during each contact, and AEs may be captured spontaneously during psychotherapy sessions, telephone calls, or other correspondence. Completed measures may create suspicion that an AE occurred; in this case, the site staff should follow-up with the participant.

All AEs will be monitored by the therapy team until resolution or, if the AE becomes chronic, a cause can be identified. If an AE is unresolved when a participant terminates from the study, a clinical assessment will be made by the site physician, investigator, and/or Medical Monitor as to whether continued follow-up of the AE is warranted.

The severity of events reported on the “Adverse Events” eCRF will be determined by the site physician as:

- Mild: No limitation in normal daily activity
- Moderate: Some limitation in normal daily activity
- Severe: Unable to perform normal daily activity

The relationship of each AE to the IMP will be determined via analysis and the opinion of the investigator will not be collected, with the exception of SAEs.

11.1.1 Adverse Events of Special Interest

In accordance with guidance for the specific study site, Health Canada Clinical Safety Data Management Definitions and Standards for Expedited Reporting ICH Topic E2A: Guidance for Industry or FDA Safety Reporting Requirements for INDs and BA/BE Studies, the sponsor will

pay special attention to a subset of AEs involving cardiac function that could be indicative of QT interval prolongation or cardiac arrhythmias, including *Torsade de pointes*, sudden death, ventricular extrasystoles, ventricular tachycardia, ventricular fibrillation and flutter, non-postural syncope, and seizures. The subset of AEs involving suicide risk under the following terms are also of special interest: suicides, suicide attempts, self-injurious behavior associated with suicidal ideation, and suicidal ideation judged to be serious or severe in the opinion of the investigator. These AEs will be marked in the eCRF with the denotation “Adverse Event of Special Interest” (AESIs) whether serious or non-serious.

In order to assess signals of abuse potential for the IMP in the intended patient population:

- AESIs involving the terms of Behavioral addiction, Drug abuser, Substance abuser, Dependence, Intentional product misuse, Overdose (accidental, intentional, or prescribed), or Drug diversion in cases that are related to MDMA or “Ecstasy” (material represented as MDMA) will be collected and coded as AESIs in the eCRF.
- Cases of noncompliance, protocol violations, participants lost to follow-up, and any other reasons why participants dropped out of the study will be assessed for presence of AESIs.
- Qualitative urine drug test data will be collected prior to each Experimental Session. Any positive findings that cannot be attributed to pre-approved concomitant medications or diet will be reviewed by the Medical Monitor to assess compliance with ongoing eligibility criteria and for presence of AESIs.

If an AESI is a SAE (Serious Adverse Event) or if it involves suicide risk, it should be reported to the sponsor with a narrative via the eCRF within 24 hours of the site’s awareness of the event.

11.1.2 Serious Adverse Events

In accordance with guidance for the specific study site, Health Canada Clinical Safety Data Management Definitions and Standards for Expedited Reporting ICH Topic E2A: Guidance for Industry or FDA Safety Reporting Requirements for INDs and BA/BE Studies, an SAE is defined as any untoward medical occurrence that at any dose:

- Results in death.
- Is life-threatening (i.e., the participant was, in the opinion of the investigator, at immediate risk of death from the event as it occurred); it does not refer to an event which hypothetically might have caused death if it were more severe.
- Requires or prolongs inpatient hospitalization.
- Results in persistent or significant disability/incapacity (i.e. the event causes substantial disruption of a person’s ability to conduct normal life functions).
- Results in a congenital anomaly/birth defect.
- Requires intervention to prevent permanent impairment or damage.
- Is an important and significant medical event that may not be immediately life-threatening or resulting in death or hospitalization, but based upon appropriate medical judgment, may jeopardize the participant or may require intervention to prevent one of the other outcomes listed above.

AEs which do not fall into these categories are defined as non-serious. It should be noted that a severe Adverse Event need not be serious in nature and that a SAE need not, by definition, be severe.

In addition, a pre-existing event or condition that results in hospitalization should be recorded on the medical history. The hospitalization would not result in the event or condition being reported as a study-related SAE, unless, in the view of the site physician, hospitalization was prolonged as a result of participation in the clinical trial or was necessary due to a worsening of the pre-existing condition. This is because the onset of the event (the reason for the procedure) occurred before the participant was entered in the trial. Hospitalization for cosmetics, non-emergency prophylaxis, or elective abortion does not result in an SAE report, unless, in the view of the site physician, hospitalization for these procedures was prolonged as a result of participation in the clinical trial.

All SAEs will be collected from enrollment through Study Termination. All SAEs which occur during the course of the trial, whether considered to be associated with IMP or not, must be reported to the sponsor within 24 hours of the site staff's awareness of occurrence. Reporting procedures will be provided to the site. All SAEs will be assessed for relationship, expectedness and any required actions to address safety at the time of reporting of the event. SAEs will be evaluated by the site physician and Medical Monitor to determine if it is appropriate for the participant to continue treatment or enter follow-up.

11.2 Other Significant Events

Significant life events that may occur during the course of the study, including death of a loved one, loss of employment, or other hardship, may have an impact on treatment outcome. The sponsor will capture these life events using the LEC-5 measure. Such events will be entered as Comments in the eCRF and if appropriate, described in the Case Study Report for data outliers, if any.

11.3 Pregnancy

11.3.1 Definition of Childbearing Potential

A participant is considered of childbearing potential if they were assigned female at birth and are post-menarche. A participant is considered not of childbearing potential if they are premenarchal, surgically sterile (documented hysterectomy, bilateral salpingectomy, bilateral oophorectomy, and/or tubal ligation), postmenopausal, or assigned male at birth.

11.3.2 Contraception Guidelines

Study participants who were assigned male at birth with partners of childbearing potential will not be required to practice birth control. Adequate birth control methods are required for participants of childbearing potential and include:

- Intrauterine device (IUD)
- Intrauterine hormone-releasing system (IUS)
- Non-oral hormonal methods, including injected, intravaginal, implanted, transdermal
- Oral hormones plus a barrier contraception (condom, diaphragm, or spermicide)
- Double barrier method (at least two of the following: condom, diaphragm, and spermicide)
- Vasectomized sole partner
- Abstinence from penile-vaginal intercourse
 - The reliability of abstinence should be evaluated carefully with the participant in relation to their general lifestyle. An additional acceptable birth control method

should be discussed with the participant in case they decide to engage in penile-vaginal intercourse during the course of the study.

For questions about acceptable birth control methods, contact the Medical Monitor.

11.3.3 Follow-up Requirements

Details of all pregnancies in study participants will be collected after Enrollment (Visit 0) and collected through 10 days after the last Experimental Session. Pregnancies should be reported to the sponsor via telephone or email within 24 hours of site staff awareness.

In the event of a pregnancy, the participant will discontinue Experimental Sessions but may continue with non-drug Integrative Sessions, the next CAPS-5 assessment, and Study Termination procedures. At a minimum, prior to withdrawal from the study, efforts should be made to assess the final CAPS-5 immediately and complete Study Termination procedures. The participant will be emergency unblinded if the participant wishes as described in [Section 9.4 Blinding](#), after the final CAPS-5 assessment.

The investigator will collect follow-up information on the participant and neonate and forward to the sponsor until the outcome of the pregnancy, which will be reported on an optional Pregnancy eCRF. Any termination, elective or spontaneous, will be reported. Abnormal pregnancy outcomes, such as spontaneous abortion, fetal death, stillbirth, congenital abnormalities, or ectopic pregnancy, will be reported as SAEs.

12.0 Concomitant Medications

12.1 Tapering Instructions

The site physician will record concomitant medications during Screening. If the prospective participant is being treated with psychiatric medications at enrollment, the prospective participant will be encouraged to discuss medication tapering with their outside treating physician, if any, and will be required to give the site physician permission to do so as well. The medications will then be tapered in an appropriate fashion to avoid withdrawal effects and will be discontinued at least five half-lives plus one additional week for stabilization before the first Experimental Session to avoid the possibility of any interaction. Additionally, participants who are taking prohibited opiates will be cross-tapered to an allowable opiate (hydrocodone, morphine, and codeine) under the care of their prescribing physician.

The site physician will consult the prescribing physician to initiate medication tapering for participants, as they must refrain from taking psychiatric medications throughout the study, with some exceptions (see [Section 12.2 Allowed Concomitant Medications](#)). The prescribing physician's opinion about medication discontinuation will be documented either in writing from the prescribing physician, or in writing by the site physician documenting phone contact with the prescribing physician. Tapering will follow a time course appropriate for the medication based on its half-life, with the Baseline CAPS-5 T1 (Visit 3) scheduled to occur after complete washout (five half-lives plus at least 1 week for stabilization).

The therapy team will request information about any changes in medication at each contact. The site physician will be responsible for reviewing and confirming all medications collected during the study.

All medications, non-prescription and prescription, will be collected from Screening through 7 days after the last Experimental Session. From 7 days after the last Experimental Session through Study Termination, only prescription or non-prescription medications taken to treat AEs will be collected. Throughout the protocol, all medications used to treat AEs will be collected, and all changes including discontinuations or additions to medications will be collected. The study team will also inquire about concomitant medication adherence and document all information on the Concomitant Medications eCRF.

Participants may return to taking psychiatric medications and discontinue birth control after the final Study Termination visit if necessary.

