3.3 Safety Objectives

The overall safety objective is to assess differences between groups in severity, incidence and frequency of Adverse Events (AEs), Treatment Emergent AEs (TEAEs), AEs of Special Interest (AESIs), and Serious Adverse Events (SAEs), concomitant medication use, suicidal ideation and behavior, and vital signs to support the package insert for MDMA-assisted psychotherapy. The following safety objectives will evaluate the safety of MDMA-assisted psychotherapy compared to identical psychotherapy with inactive placebo:

1. Compare relative incidence of AEs during Experimental Sessions that may be indicative of a medical complication of the Investigational Medicinal Product (IMP) such as clinical signs and symptoms of chest pain, shortness of breath, or neurological symptoms or any other signs or symptoms that prompt additional vital sign measurements.
2. Compare relative incidence of AEs by severity.
3. Compare relative incidence of TEAEs, to determine relationship to the IMP based on relative incidence in the MDMA group.
4. Compare relative incidence of TEAEs by severity reported during an Experimental Session, 1 day, and 2 days after IMP administration.
5. Compare relative incidence of AESIs, defined as AEs specified in the protocol related to cardiac function and abuse liability.
6. Compare relative incidence of AEs by severity categorized as leading to discontinuation of IMP, resulting in death or hospitalization, and continuing at Study Termination.
7. Compare relative incidence of SAEs.
8. Compare relative incidence of concomitant medications taken during an Experimental Session, 1 day, and 2 days after IMP administration.
9. Compare relative incidence of psychiatric concomitant medications taken during the Treatment Period.
10. Compare relative incidence of positive or serious suicidal ideation and positive suicidal behavior assessed with the Columbia Suicide Severity Rating Scale (C-SSRS) by treatment group.
11. Compare mean changes in blood pressure, heart rate, and body temperature from pre-IMP administration to end of each Experimental Session by treatment group.

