8.4 Follow-up Period and Study Termination

8.4.1 Follow-up Period

After the last Integrative Session 3.3 (Visit 18), participants will enter follow-up for approximately 4 weeks (± 2 weeks) with no protocol required visits until the final CAPS-5 assessment (Visit 19) followed by Study Termination (Visit 20). Participants will have access to therapy teams for support if needed, and additional visits via phone, telemedicine, or in person can be scheduled if requested. Participants will continue to comply with protocol requirements for concomitant medications until after Study Termination.

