12.2 Allowed Concomitant Medications

The site physician may prescribe necessary and appropriate medications in accordance with local and state regulations during the study to treat AEs that do not respond to other management outlined in the Treatment Manual. Examples include concomitant benzodiazepines for uncontrolled anxiety (for example, lorazepam at modest doses and occasional use only to avoid withdrawal effects of discontinuation between Experimental Sessions) or sleep aids (excluding trazodone) in compliance with [Section 12.3 Prohibited Medications](#). Sublingual nitroglycerin will be available on site in the case of emergency.

Gabapentin or certain opiates will be allowed when prescribed for pain management. The following opiates will be allowed during the study: hydrocodone, morphine, and codeine. Prior to randomization, participants who are taking opiates not included on this list will be cross-tapered to an allowable opiate under the care of their prescribing physician. Opiate medications may reduce the efficacy of MDMA and may prolong QT/QTc interval, but the opiates that are allowed during this trial have been selected because they have the lowest potential for QT/QTc interval prolongation and minimal serotonergic effects. Individuals using opiates for pain management will be asked to decrease the dose leading up to the Experimental Session in order to avoid withdrawal effects when they are required to refrain from taking the medication from 12 hours before IMP administration at the Experimental Session to 24 hours after. If a participant reports lack of analgesic effect during the sub-acute period following each Experimental Session, the site physician may approve taking an allowed opiate medication sooner than 24 hours after IMP administration.

If the participant is on stimulants for Attention Deficit/Hyperactivity Disorder (ADHD) at Baseline, they can continue to use them at the same dose and frequency, as long as they discontinue five half-lives before each Experimental Session and do not restart for 10 days after each Experimental Session.

All psychoactive medications, herbal supplements, nonprescription medications, and prescription medications must be reviewed by the research team at least 2 weeks prior to each Experimental Session. Failure to comply with protocol requirements for concomitant medications may result in withdrawal from treatment, depending on the investigator and Medical Monitor judgment.

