12.3 Prohibited Medications

To be enrolled in the study, participants must:

- Refrain from the use of any psychoactive medication not approved by the research team from Baseline through Study Termination (with the exception of gabapentin or certain opiates for pain control).
- Be willing to comply with all medication requirements per protocol. Medications will only be discontinued after enrollment per clinical judgment of the site physician in consultation with the prescribing physician.
- Agree that, for 1 week preceding each Experimental Session they will refrain from:
 - Taking any specified herbal supplement (except with prior approval of the research team).
- Agree that, for 5 half-lives of the medication preceding each Experimental Session they will refrain from:
 - Taking any nonprescription medications (with the exception of non-steroidal anti-inflammatory medications or acetaminophen) unless with prior approval of the research team.
 - Taking any prescription medications (with the exception of birth control pills, thyroid hormones, or other medications approved by the research team).

Use of Marijuana, St. John's Wort, and other herbs and medicines with notable serotonergic effects are prohibited from Baseline to Study Termination. Any investigational treatments under study for PTSD treatment are prohibited from use concurrent with this study.

Diphenhydramine is excluded from this study unless prior approval is granted by the site physician.

If an SSRI, SNRI, MAOI, or other antidepressant is used between Experimental Session 1 (Visit 5) and Study Termination (Visit 20), the participant will discontinue study treatment and continue in follow-up. Participants whose Experimental Sessions are delayed by the COVID-19 pandemic may start any of these medications during the delay, as clinically indicated. When study visits resume, they will be given the option to resume Experimental Sessions after tapering off of these medications, per the tapering plan described above.

Opiates other than hydrocodone, morphine, and codeine are prohibited from Enrollment Confirmation to Study Termination. Participants taking prohibited opiates will be cross-tapered to an allowable opiate prior to Experimental Sessions.

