14.2.2 Safety Analyses

Safety analyses will confirm safety data with summary tables listing exposure to IMP, unsolicited AEs, concomitant medications, suicidal ideation and behavior, and vital signs overall and by group. If a participant has more than one AE mapped to the same PT, that AE will be reported once using the highest severity. AEs that occur on Day 0 (Experimental Session), Day 1, Day 2 after IMP administration will be presented separately. Compare relative incidence of AEs during Experimental Sessions such as clinical signs and symptoms, such as chest pain, shortness of breath, or neurological symptoms or any other signs or symptoms that may be indicative of a medical complication of the IMP.

Frequency and incidence of concomitant medications will be displayed by generic name, sorted by class, and summarized by treatment group, analysis set, and category. Concomitant medications taken on Day 0 (Experimental Session), Day 1, Day 2 after IMP administration will be presented separately. Any psychiatric concomitant medications will be tabulated by period (Preparatory, Treatment Period, Follow-up Period). Frequency and incidence of positive or serious ideation and suicidal behavior will be presented using descriptive statistics of C-SSRS scores in tabular format. Vital signs (heart rate, blood pressure, and body temperature) for Experimental Sessions will be summarized using descriptive statistics in tabular format listing values at pre-IMP administration, prior to the supplemental dose, and at the end of each Experimental Session by treatment group. Additional details are available in the Statistical Analysis Plan.

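### Protocol 12.1 gives two conflicting rules for collecting medication from day 7 after the last Experimental Session, so non-AE psychiatric medication that planned safety tables need may go unrecorded

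*Protocol*

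**What the plan says.** Protocol 12.1 sets full collection, prescription and non-prescription, from Screening to day 7 after the last Experimental Session. It then narrows the rule: "From 7 days after the last Experimental Session through Study Termination, only prescription or non-prescription medications taken to treat AEs will be collected". The following sentence says that throughout the protocol AE treatments are collected and "all changes including discontinuations or additions to medications will be collected", with no limit to AE treatment. The paragraph closes by having the team ask about adherence and "document all information on the Concomitant Medications eCRF".

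Other parts of the plan concern medication taken after that day:

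- **Protocol 12.3:** for an antidepressant of any class, when "used between Experimental Session 1 (Visit 5) and Study Termination (Visit 20), the participant will discontinue study treatment and continue in follow-up". Section 8.4.1 adds: "Participants will continue to comply with protocol requirements for concomitant medications until after Study Termination".
- **Protocol 3.3, safety objective 9:** "Compare relative incidence of psychiatric concomitant medications taken during the Treatment Period". SAP 8.8.3 ends that period at the last Integrative Session, which is Visit 18.
- **Protocol 14.2.2 and SAP 8.8.3:** psychiatric medications are tabulated by period, and the Follow-up Period is one of the periods. SAP 8.8.3 lists medications taken for an AE as a separate category, so the psychiatric table is not confined to AE treatment.
- **Protocol 12.2:** participants on ADHD stimulants at Baseline may keep using them if they stop five half-lives before each session and "do not restart for 10 days after each Experimental Session".

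**The concern.** A collection rule decides what reaches the database, and no analysis can later restore what was not collected. SAP 8.8.3 classifies the medications that were collected; it does not widen collection. If some sites follow one sentence and some the other, the psychiatric medication tables will be incomplete to an extent that varies by site and that nobody can see from the data. At stake are the Follow-up Period psychiatric medication table, the last part of the safety objective 9 window, and the record of non-AE antidepressant use late in the study. For participants who stop after an early session, knowledge of rescue medication in SAP Table 5 is also at stake.

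**Working it through.** No planned figure is in dispute, so the check is a comparison of wording followed by day counts from the visit windows.

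**1. The two sentences applied to the same cases (after day 7)**

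| Medication | AE-only sentence | All-changes sentence |
|---|---|---|
| Drug for worsening PTSD (an AE, since Protocol 11.1 includes exacerbation of a pre-existing condition) | collected | collected |
| Antidepressant restarted for unchanged PTSD | not collected | collected |
| ADHD stimulant resumed after Visit 15 | not collected | collected |
| Background drug recorded before day 7 and unchanged | already on record | already on record |

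The conflict is confined to rows two and three. In the stimulant case, SAP 8.8.3 expects a stop date before each session for a drug that has to be interrupted. The earlier record is then closed, and resumption needs a new entry.

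**2. Length of the AE-only window for a participant given three sessions**

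Inputs, with Visit 15 as day 0: Visit 18 on day 21 to 35 (Protocol 8.3.3); Visit 19 on day 42 to 70 (8.4.2); Visit 20 1 to 9 days after Visit 19 (8.4.3); Visits 5 to 10 and Visits 10 to 15 each 21 to 35 days apart (8.3.1).

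- To Visit 20: 42 + 1 − 7 = 36 days, up to 70 + 9 − 7 = 72 days.
- Part inside the Treatment Period: 21 − 7 = 14 days, up to 35 − 7 = 28 days.
- Share of the Treatment Period (Visit 5 to Visit 18): smallest 14 / (35 + 35 + 21) = 14/91 = 15%; largest 28 / (21 + 21 + 35) = 28/77 = 36%. At 28-day spacing it is (28 − 7) / 84 = 25%.
- Follow-up Period: it begins at Visit 18, on day 21 at the earliest, so all of it lies after day 7.
- Stimulants: the earliest permitted restart is day 10, so every restart after Visit 15 falls in the window. Day 10 to Visit 18 is 21 − 10 = 11 days, up to 35 − 10 = 25 days.

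**3. A participant who stops after Session 1**

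The last Experimental Session is then Visit 5, 4 to 7 days after Visit 3. Assuming follow-up on schedule to Visit 19, 105 to 147 days after Visit 3, the window before Visit 19 is 105 − 7 − 7 = 91 days, up to 147 − 4 − 7 = 136 days.

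SAP Table 5 separates discontinuation with and without rescue medication. In the placebo arm both rows prescribe the same imputation. In the MDMA arm both rows use the same two methods; they differ in whether the CAPS and the reason, or the reason alone, decide between them. The table serves a sensitivity analysis only.

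**The case against.** The strongest reply is that the paragraph can be read as a whole. Full listing of unchanged background drugs stops at day 7, while AE treatments and every start, stop or restart continue to be collected. Both exposed cases are changes, so on that reading neither is lost. Sites ask about medication at Visits 16 to 18 and 20 and are told to put what they learn on the eCRF. Prohibited antidepressant use is also a deviation, summarised under SAP 8.3 and 8.8.3. Much of this stands: many cases would be caught. But the protocol does not state that reading. A site must choose it against a sentence containing the word only, and a deviation summary shows only what was recorded. Permitted stimulant use is not a deviation at all.

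The reply is also right that stimulants matter little for safety objective 9. That objective concerns incidence over the whole Treatment Period. Someone who resumed between earlier sessions is already counted; only a first restart after Visit 15 could be missed. The Follow-up Period table is more exposed.

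A reader might infer more than the documents support:

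- **That 15% to 36%, or all of the Follow-up Period, is lost data.** These are shares of calendar time. The documents give no rate of non-AE psychiatric medication use.
- **That the primary result is affected.** The month rated by the CAPS-5 at Visit 19 does fall inside the window: with a 31-day month it starts on day 42 − 31 = 11 at the earliest. But no planned analysis uses medication exposure in that month, and after Visit 15 no session remains for 12.3 to withhold from a completer.
- **That a planned comparison of late antidepressant use by arm would fail.** The plan contains no count by arm of use starting after Visit 15.

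**Conclusion.** The inconsistency is real, and the text is wrong as written, at low severity. From day 7 after the last Experimental Session, consecutive sentences give opposite instructions for a newly started non-AE medication. If the AE-only sentence is followed, the collected data cannot fully support the Follow-up Period psychiatric medication table or the last 14 to 28 days of the safety objective 9 window, and non-AE antidepressant use that 12.3 governs to Visit 20 may not be seen. For early stoppers the window is longer and could blur the rescue-medication rows of SAP Table 5.

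This rests on two assumptions: that some sites apply the AE-only sentence as written, and that some participants take psychiatric medication for a reason that is not an AE. The documents allow both but quantify neither, so the number of missed records cannot be estimated. No sample size, power or alpha figure changes.

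**What to change.** Amend Protocol 12.1 so that every psychiatric and every prohibited medication, and every start or stop of one, is recorded with dates and reason through Visit 20, whether or not it treats an AE. Limit the AE-only sentence to other medications, and match the eCRF instruction to this. For psychiatric and prohibited drugs the restricted window then falls from 36 to 72 days to zero.

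The cost is one amended sentence, one eCRF instruction and a little more data entry. No visit is added. Participants already terminated would need queries, and what was not recorded for them may not be fully recoverable.

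Two additions are optional and not part of the error: a date split, by arm, of antidepressant use starting after Visit 15 within the excluded-medication summary of SAP 8.8.3, and one SAP sentence saying that a Visit 19 score obtained after such use stays in Estimand 1.
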